13. VIROLOGY

The virology analyses will mainly use genotype and phenotype data based on plasma sample for CVF population, unless otherwise specified. Additional analyses for HIV-1 resistance may be carried out on peripheral blood mononuclear (PBMC) samples collected at Day 1, Week 48, Week 96, Week 152 or Withdrawal if prior to Week 152, Sub-study Day 1.

If pre-treatment genotypic/phenotypic results are available from both the central laboratory and Monogram Biosciences, then Baseline genotype/phenotype will be determined based only upon the data provided by Monogram assays.

Table 7 provides an overview of the planned analyses, with further details of data displays being presented in [Appendix 15: List of Data Displays](#).

Table 7 Overview of Planned Virology Analyses

| Endpoint | Absolute | | | |
|---|------------------|---|------------|------------------|
| | Summary | | Individual | |
| | T | F | F | L |
| Genotypic resistance at time of CVF^[1] | | | | |
| Prevalence of Resistance Mutations | Y ^[2] | | | Y |
| Prevalence of Genotypic Susceptibility | Y | | | |
| Phenotypic resistance at time of CVF^[1] | | | | |
| Prevalence of Phenotype | Y ^[3] | | | Y |
| Fold Change to CAB and RPV | Y | | | Y ^[4] |
| IN, PR/RT Replication Capacity | | | | Y |
| Other | | | | |
| Viral load, Genotypic and Phenotypic data for Participants with genotype and/or phenotype data for CVF and non-CVF participants | | | | Y ^[4] |
| Net Assessment | Y | | | |

NOTES:

- T = Table, F = Figure, L = Listing, Y = Yes display generated.
- Summary = Represents TFL related to any summaries (i.e. descriptive statistics) of the observed raw data.
- Individual = Represents FL related to any displays of individual participant observed raw data.

1. For the CVF as indicated by two consecutive plasma HIV-1 RNA levels ≥ 200 c/mL after prior suppression to < 200 c/mL, the first visit of these two consecutive visits is defined as 'the suspected visit', and the 2nd one is the confirmed visit. Sample used for resistance testing is taken at the suspected visit, and only tested once a participant confirms virological failure at a subsequent visit. If the test fails with the sample at the suspected visit, we will just report it as 'no data'. The sample from the confirmed visit may be used for exploratory analyses.
2. No. and percentage of participants with IN resistance mutations or major mutations in the classes of NNRTI, NRTI, PI, respectively, as defined in Section [15.6.7](#).
3. Separate outputs by phenotypic susceptibility and by number of drugs to which participants are phenotypic resistant or partial sensitive or sensitive.

| Endpoint | Absolute | | | |
|----------|----------|---|------------|---|
| | Summary | | Individual | |
| | T | F | F | L |

4. Fold change to CAB and RPV will be included in the listing for viral load, genotypic and phenotypic data for participants with genotype and/or phenotype data for CVF and non-CVF participants.

15. APPENDICES

15.1. Appendix 1: Protocol Deviation Management and Definitions for Per Protocol Population

15.1.1. Exclusions from Per Protocol Population

Important protocol deviations leading to exclusion from the Per Protocol population are those deviations which may

- directly impact the efficacy endpoint of HIV-1 RNA; or
- lead to permanent discontinuation of IP/withdrawal and hence indirectly impact the efficacy endpoint by causing data to be missing.

The following criteria define the important protocol deviations which, if they occur prior to an analysis timepoint of interest (e.g. Week 48/96/152), will lead to exclusion of a participant from the Per-Protocol population for that analysis. Potential protocol deviations leading to exclusion from PP population will be reviewed by the study team to confirm that they meet these criteria. A final review will occur before the clinical database has been frozen for analysis.

A participant meeting any of the following criteria will be excluded from the Per Protocol population based on case-by-case clinical determination:

| Number | Exclusion Description |
|--------|--|
| 01 | Participant deviates from any inclusion or exclusion criteria that may significantly affect exposure, response to therapy or participant safety or that are fundamentally inconsistent with the intended study population, as recorded in the Protocol Deviation form in the eCRF based on study team review (where indicated in the PDMP as case-by-case determination). |
| 02 | 
Participant has maintenance phase non-compliance (including IM dosing errors) with investigational product up to an analysis timepoint of interest, meeting one of the following 3 conditions. For Week 48 analysis, the analysis timepoint of interest is the date of last on-treatment viral load up to Study Day 378 during maintenance phase, where Study Day 378 is the upper bound of snapshot window for Week 48 visit. For Week 96 analysis, the analysis timepoint of interest is the date of last on-treatment viral load up to Study Day 714 during the maintenance phase, where Study Day 714 is the upper bound of snapshot window for Week 96 visit. For Week 152 analysis, the analysis timepoint of interest is the date of last on-treatment viral load up to Study Day 1106 during the maintenance and extension phase, where Study Day 1106 is the upper bound of snapshot window for Week 152 visit.
 
1. Week 48 analysis only:
 
 • Two or more injection intervals affected by over dosage deviations, for example 
 ◦ Extra injection or excessive volume administered. ◦ For Q8W participants requiring oral lead-in: length of time between Week 4B injection and Week 8 injection less than 3 weeks, or between injections post Week 8 less than 7 weeks, excluding split doses. ◦ For Q8W participants not requiring oral lead-in: length of time between injections less than 7 weeks, excluding split doses. |

| Number | Exclusion Description |
|--------|--|
| | 
 ○ For Q8W participants requiring reloading injections: length of time between the reloading injection and the injection after reloading less than 3 weeks, excluding split doses. ○ For Q4W participants: length of time between injections less than 3 weeks, excluding split doses. 
2. Week 96 analysis only:
 
 • For participants who permanently discontinued study treatment on/before the analysis timepoint of interest for Week 48 analysis (i.e. the date of last on-treatment viral load up to Study Day 378): two or more injection intervals affected by over dosage deviations. • For participants who received injections beyond the analysis timepoint of interest for Week 48 analysis (i.e. the date of last on-treatment viral load up to Study Day 378): three or more injection intervals affected by over dosage deviations. 
3. Week 152 analysis only:
 
 • For participants who permanently discontinued study treatment on/before the analysis timepoint of interest for Week 48 analysis (i.e. the date of last on-treatment viral load up to Study Day 378): two or more injection intervals affected by over dosage deviations. • For participants who received injections beyond the analysis timepoint of interest for Week 48 analysis (i.e. the date of last on-treatment viral load up to Study Day 378): five or more injection intervals affected by over dosage deviations. 
4. $\geq 10\%$ of total time on-treatment with under dosing deviations. The percentage of total time on-treatment with under dosing deviations will be calculated by (the total number of non-compliant dosing days / the total number of intended exposure days) * 100%.
 
Number of Intended Exposure Days = Date of Last Viral Load – Start Date of Study Treatment + 1, where the last viral load refers to the last on-treatment viral load up to Study Day 378 during maintenance phase for Week 48 analysis, the last on-treatment viral load up to Study Day 714 during maintenance phase for Week 96 analysis, the last on-treatment viral load up to Study Day 1106 during maintenance and extension phase for Week 152 analysis .
 
The total number of non-compliant dosing days up to the analysis timepoint visit (or date of IP discontinuation/ withdrawal, whichever is earlier), is derived as follows (summing across all instances):
 
 • For Q4W arm participants requiring oral lead-in: 
 ○ Length of time (in days) until next injection from date of dosage deviation (e.g. 2 mL administered instead of 3mL for Week 4B injection, 1ml administered instead of 2 mL for post Week 4B injections). ○ Length of time (in days) in excess beyond 35 days between injections post Week 12 and in excess beyond 28 days for Week 8 and Week 12 (e.g. missed or late injection visit). ○ Length of time (in days) in excess beyond 35 days from last injection until start of oral bridging post Week 12 and in excess beyond 28 days for Week 8 and Week 12. • For Q4W arm participants not requiring oral lead-in: |

| Number | Exclusion Description |
|--------|---|
| | 
 ○ Length of time (in days) until next injection from date of dosage deviation (e.g. 1 mL administered instead of 2 mL). ○ Length of time (in days) in excess beyond 35 days between injections. ○ Length of time (in days) in excess beyond 35 days from last injection until start of oral bridging. ● For Q8W arm participants requiring oral lead-in: 
 ○ Length of time (in days) until next injection from date of dosage deviation (e.g. 2 mL administered instead of 3mL). ○ Length of time (in days) in excess beyond 63 days between injections post Week 16 and in excess beyond 28 days for Week 8 and 56 days for Week 16 (e.g. missed or late injection visit). The similar calculation of the length of time in excess will be used for the period after the reloading dose injection visit. ○ Length of time (in days) in excess beyond 63 days from last injection until start of oral bridging post Week 16 and in excess beyond 28 days for Week 8 and 56 days for Week 16. ● For Q8W arm participants not requiring oral lead-in: 
 ○ Length of time (in days) until next injection from date of dosage deviation (e.g. 2 mL administered instead of 3 mL). ○ Length of time (in days) in excess beyond 63 days between injections. ○ Length of time (in days) in excess beyond 63 days from last injection until start of oral bridging. ● For subjects requiring reloading injections, the number of non-compliant days for the first and second injection visits after the reloading will be calculated similarly to that for Week 8 and Week 12 for subjects on the same treatment arm requiring oral lead-in. ● Interrupted days in oral study treatment (oral lead-in or oral bridging) if the oral dose has been interrupted for 3 or more consecutive days and the primary interruption reason is not adverse event or laboratory abnormality (based on the eCRF Exposure forms). 3 days will be assumed if such interrupted days are not available in the database. |
| 03 | Prohibited medications: receiving ART medication other than that prescribed/allowed by the study (excluding permanent changes in ART regimen; such cases will be retained as 'HIV1- RNA ≥ 50 c/mL' in the per protocol snapshot analysis) or receiving prohibited concomitant medication that would impact exposure or response to therapy with duration and route of administration taken into consideration, as recorded in the Protocol Deviation form in the eCRF based on study team review (where indicated in the PDMP as case-by-case determination). |
| 04 | Permanent discontinuation of IP/withdrawal due to a reason of "Protocol Deviation" (as recorded in the eCRF). |
| 05 | Other important protocol deviations that exclude Participant from per protocol population as recorded in the Protocol Deviation form in the eCRF based on study team review (where indicated in the PDMP as case-by-case determination). The participants who has taken SOC oral bridging at/prior to the analysis timepoint due to COVID-19 may be excluded from per protocol population for the analysis and will be evaluated based on case-by-case clinical determination. |

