During the maintenance and extension phase, the planned nominal visits for PK Pre-dose are Week 4B, 8, 16, 24, 32, 40, 48, 96, 152 for Q4W arm; and are Day 1, Week 4B, 8, 16, 24, 32, 40, 48, 96, 152 for Q8W arm while Day 1 is required only for those transitioning from ATLAS on Q4W injections and Week 4B is required only for participants transitioning from oral SOC and requiring oral CAB+RPV lead-in. In addition, the participants on Q8W arm have planned nominal visits at Week 9 and 41 for 1-week post-dose.

For participants requiring oral CAB+RPV lead-in, the planned injection visits are Week 4B, Week 8, continuing every 4 weeks for Q4W arm and continuing every 8 weeks for Q8W arm. For participants not requiring oral CAB+RPV lead-in, the planned injection visits are every 4 weeks starting from Day 1 for Q4W arm and every 8 weeks starting from Day 1 for Q8W arm.

Example 1: If a participant on Q8W arm has the 'last nominal visit' (with PK pre-dose assessment) at Week 24 and then withdraws around Week 28, with the last injection at Week 24 and a Maintenance Phase PK assessment labelled at 'LTFU Month 1', This PK assessment labelled as 'LTFU Month 1' will be slotted to the subsequent planned nominal visit of Week 32.

Example 2: If a participant on Q4W arm has the 'last nominal visit' (with PK pre-dose assessment) at Week 48 and then have an unscheduled Maintenance Phase PK assessment around Week 74. This assessment will be slotted to the next planned injection visit, Week 76.

There will be no slotting for planned nominal visits (i.e. analysis visit =visit).

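### The Week 152 over-dosage exclusion has no tier for participants who stopped between the Week 48 and Week 96 timepoints, so some excluded at Week 96 re-enter the Per-Protocol population on unchanged dosing data

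*SAP*

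**What the plan says.** Criterion 02 in SAP Section 15.1.1 (Appendix 1) lists the dosing deviations that remove a participant from the Per-Protocol population. Items 1 to 3 deal with over-dosage, one item per analysis.

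- **Item 1, Week 48:** "Two or more injection intervals affected by over dosage deviations", for everyone.
- **Item 2, Week 96:** two groups. The first is defined as "For participants who permanently discontinued study treatment on/before the analysis timepoint of interest for Week 48 analysis" and keeps the cut-off of two. The second is defined as "For participants who received injections beyond the analysis timepoint of interest for Week 48 analysis" and has a cut-off of "three or more injection intervals affected by over dosage deviations".
- **Item 3, Week 152:** the same two groups, divided again at the Week 48 timepoint. The first keeps the cut-off of two. The second has a cut-off of "five or more injection intervals affected by over dosage deviations".

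The analysis timepoint is the date of the last on-treatment viral load up to Study Day 378 for Week 48, Day 714 for Week 96 and Day 1106 for Week 152. For Week 96 the SAP notes that "Study Day 714 is the upper bound of snapshot window for Week 96 visit".

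**The concern.** The cut-off rises because a participant followed for longer has more opportunity for dosing deviations. Items 2 and 3 recognise the corollary: someone who stopped by the Week 48 timepoint gained no further opportunity and should not receive the later, looser limit. Item 3 applies that principle at Week 48 but not at Week 96. A participant who stopped between the two timepoints gains no exposure after Week 96, yet the limit moves from three to five.

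The Per-Protocol analysis is there to be compared with the ITT-E result for consistency (SAP Sections 5.5.2 and 7.1.5.1). It is planned at Week 152 for both snapshot endpoints (SAP Section 15.15.6.2, Tables 2.2 and 2.9). If a participant's status reverses between Week 96 and Week 152 with no change in dosing, part of any difference between the two Per-Protocol analyses comes from the wording of the rule.

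**Working it through.** The SAP gives no derivation for the cut-offs of two, three and five, so there is no stated figure to reproduce. The check applies items 2 and 3 as written and then asks whether the underlying data can differ between the two analyses.

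**Step 1. The over-dosage rule by time of stopping.**

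| Stopped treatment | Affected intervals | Week 96 | Week 152 |
|---|---|---|---|
| On/before Week 48 timepoint | 1 | kept (cut-off 2) | kept (cut-off 2) |
| On/before Week 48 timepoint | 2 or more | excluded | excluded |
| Between Week 48 and Week 96 timepoints | 1 or 2 | kept (cut-off 3) | kept (cut-off 5) |
| Between Week 48 and Week 96 timepoints | 3 or 4 | **excluded** | **kept** |
| Between Week 48 and Week 96 timepoints | 5 or more | excluded | excluded |

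Only the row with three or four affected intervals reverses.

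**Step 2. Are the data the same at both analyses?** Inputs: the nominal study day for week w is 7w + 1 (SAP Section 15.3.1). On-treatment time ends 63 days after the last injection in Q8W and 35 days after it in Q4W, if no oral treatment follows (SAP Section 15.4.2, Table 20). The last scheduled injection before Week 96 is Week 88 in Q8W and Week 92 in Q4W.

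- Q8W: 7 × 88 + 1 = 617, and 617 + 63 = Day 680.
- Q4W: 7 × 92 + 1 = 645, and 645 + 35 = Day 680.

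Day 680 is before Day 714. For these participants the last on-treatment viral load up to Day 714 is also the last one up to Day 1106. The count of affected intervals up to that date is the same too.

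**Step 3. An example of the resulting order.** Take two Q8W participants without oral lead-in.

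- A has a last injection at Week 56 (Day 7 × 56 + 1 = 393, beyond Day 378), with 4 of 7 completed eight-week intervals affected: 4/7 = 57%. At Week 152, 4 is below 5, so A is kept.
- B stopped at the Week 48 timepoint with 2 of 6 intervals affected: 2/6 = 33%. At Week 152, 2 meets the cut-off of 2, so B is excluded.

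**Step 4. With a middle tier.** If a cut-off of three applied at Week 152 to those who stopped on or before the Week 96 timepoint, the row with three or four intervals would read excluded at both analyses. No other row changes.

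**The case against.** Three points can be made in defence of the text.

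First, exclusion is not mechanical. Section 15.1.1 makes it subject to case-by-case clinical determination, and criterion 05 allows other important deviations to be added. This stands in part: an individual could still be removed by the under-dosing item or by criteria 01, 03, 04 or 05. However, the case-by-case review is of participants who meet a written criterion, and at Week 152 this group does not meet the over-dosage one.

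Second, Per-Protocol membership is meant to vary by analysis; Section 15.1.1 defines exclusion separately for each timepoint. That also stands. A reader might infer that any change of status between analyses is a fault, but the SAP does not support that. A participant who continues beyond Week 96 with three or four affected intervals also becomes eligible at Week 152, but with more exposure behind the count, which is what a rising cut-off is for. The anomaly is confined to those who stopped between the two timepoints.

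Third, the analysis concerned is a sensitivity analysis at a secondary timepoint. That is correct and limits the importance of the point.

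**Conclusion.** The gap is real and follows directly from the wording of item 3. It affects the Week 152 Per-Protocol analysis only, and only participants who stopped between the Week 48 and Week 96 timepoints with three or four affected intervals. Their number is not in the document and is probably small. The claim that the data are unchanged assumes on-schedule dosing; oral bridging or late injections could carry on-treatment data past Day 714 in isolated cases. The ITT-E analyses are not affected. This is a minor correction.

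A stronger reading is tempting. Where no oral lead-in is needed, the schedule reads "the planned injection visits are every 4 weeks starting from Day 1 for Q4W arm and every 8 weeks starting from Day 1 for Q8W", so the same count is a smaller share of a Q4W participant's intervals. A reader might infer that the counts bias the Per-Protocol population against Q4W and should become a share of on-treatment time. The documents do not support this. Counting dosing errors is an ordinary Per-Protocol criterion, and criterion 02 already defines over-dosage separately by arm (for example, injections less than 3 weeks apart in Q4W and less than 7 weeks apart in Q8W after any loading period). The SAP gives no per-interval error rate, so any stated difference in exclusion rests on an assumption.

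A share-of-time rule is not neutral either. Assume, for illustration, an independent 2% risk per interval, with 12 Q4W and 6 Q8W intervals by Week 48. The present count of two excludes 1 − 0.98^12 − 12 × 0.02 × 0.98^11 = 2.3% of Q4W and 1 − 0.98^6 − 6 × 0.02 × 0.98^5 = 0.57% of Q8W. A cut-off at 10% of time needs two Q4W intervals (2/12 = 16.7%; one is 8.3%) but only one Q8W interval (1/6 = 16.7%). It would exclude 2.3% of Q4W and 1 − 0.98^6 = 11.4% of Q8W. The imbalance reverses, so that change is not recommended.

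**What to change.** In SAP Section 15.1.1, criterion 02, item 3, replace the two groups with three:

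- stopped on or before the Week 48 timepoint: two or more affected intervals (unchanged);
- injected beyond the Week 48 timepoint but permanently discontinued on or before the Week 96 timepoint (last on-treatment viral load up to Study Day 714): three or more;
- injected beyond the Week 96 timepoint: five or more.

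Items 1, 2 and 4 stay as they are. The introduction to criterion 02 refers to three conditions where four are numbered, which can be corrected in the same edit.

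The cost is one added sentence and one added condition in the Week 152 Per-Protocol derivation; a few participants may change status. If the Week 152 Per-Protocol results already exist, list the participants in the middle group with three or four affected intervals and report the re-run alongside the original.

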15.2. Appendix 2: Schedule of Activities

While some assessments included in the Time and Events Table are conducted less frequently following the primary endpoint (Week 48), IM injections for participants during the Extension Phase will continue to be administered Q4W or Q8W based on original study randomization assignment.

All patients will be randomized at Day 1 to initiate either Q4 weekly or Q8 weekly administration of IM CAB LA + RPV LA. Only participants randomized from oral SOC treatment will participate in the Day 1 to Week 4 Oral CAB + Oral RPV lead-in treatment.

15.2.1. Protocol Defined Schedule of Events for Q4W Arm in Main Study

| Procedure | Screening Visit ^a | Maintenance Phase | | | | | | | | | | | | | | Extension Phase | | Withdrawal Assessments, ^y | Long-Term Follow-up ^z | | | | |
|---|------------------------------|--|----------------|------|----|----|----|----|----|----|----|----|----|----|----|-----------------|-----------|--------------------------------------|----------------------------------|--------------------|-------------------|-----|--|
| | | Day 1 | | Week | | | | | | | | | | | | | | | | | | | |
| | | Week 4A (Oral Lead-in Only) ^b | Week 4B | 8 | 12 | 16 | 20 | 24 | 28 | 32 | 36 | 40 | 44 | 48 | 52 | Q4W 56-92 | Q8W 56-92 | 96 | 100 | Q4W After Week 100 | Q8W After Week 96 | 152 | |
| Written informed consent | X | | | | | | | | | | | | | | | | | | | | | | |
| Eligibility Verification (Inclusion/Exclusion Criteria) | X | | X ^c | | | | | | | | | | | | | | | X ^c | | | | | |
| Randomization | | X | | | | | | | | | | | | | | | | | | | | | |
| Demography | X | | | | | | | | | | | | | | | | | | | | | | |
| Medical History ^d | X | | | | | | | | | | | | | | | | | | | | | | |
| Cardiovascular risk assessment ^d | X | X | | | | | | | | | | | | | | | | | | | | | |
| Medication History/ Prior ART history | X | | | | | | | | | | | | | | | | | | | | | | |
| Syphilis serology + Reflex Rapid Plasma Reagin (RPR) | X | X | | | | | | | | | | | | | | | | | | | | | |

CONFIDENTIAL

207966

| Procedure | Screening Visit ^a | Maintenance Phase | | | | | | | | | | | | | | | | | | | | Extension Phase | | Withdrawal Assessments ^y | Long-Term Follow-up ^z | | |
|---|------------------------------|---|---------|------|----|----|----|----|----|----|----|----|----|----|----|--------------|--------------|----|-----|-----------------------|----------------------|-----------------|---|-------------------------------------|----------------------------------|---|--|
| | | Day 1 | | Week | | | | | | | | | | | | | | | | | | | | | | | |
| | | Week 4A (Oral Lend-in Only) ^b | Week 4B | 8 | 12 | 16 | 20 | 24 | 28 | 32 | 36 | 40 | 44 | 48 | 52 | Q4W 56-92 | Q8W 56-92 | 96 | 100 | Q4W After Week 100 | Q8W After Week 96 | 152 | | | | | |
| Symptom Directed Physical Exam and Medical Assessment ^e | X | X | X | X | X | X | X | X | X | X | X | X | X | X | X | X | X | X | X | X | X | X | X | X | X | X | |
| Weight, Height and BMI ^f | | X | | | | | | | | | | | | | | X | | | X | | | | X | X | | | |
| Vital Signs: BP, HR, Temperature ^g | X | X | | | | | | | | | | | | | | X | | | X | | | | X | X | | | |
| 12-lead ECG ^h (triplicate at Day 1 pre-dose) | X | X | | | | | | | | | | | | | | X | | | X | | | | X | X | | | |
| CDC HIV-1 stage | X | X | | | | | | | | | | | | | | | | | | | | | | | | | |
| HIV Associated Conditions | | X | X | X | X | X | X | X | X | X | X | X | X | X | X | X | X | X | X | X | X | X | X | X | X | X | |
| AEs, SAEs, Concomitant Medications ⁱ | X | X | X | X | X | X | X | X | X | X | X | X | X | X | X | X | X | X | X | X | X | X | X | X | X | X | |

| Procedure | Screening Visit ^a | Maintenance Phase | | | | | | | | | | | | | | | | | | | | Extension Phase | Withdrawal Assessments ^y | Long-Term Follow-up ^z | | | |
|---|------------------------------|--|---------|------|----|----|----|----|----|----|----|----|----|----|----|--------------|--------------|----|-----|-----------------------|----------------------|-----------------|-------------------------------------|----------------------------------|---|--|--|
| | | Day 1 | | Week | | | | | | | | | | | | | | | | | | | | | | | |
| | | Week 4A (Oral Liquid Only) ^b | Week 4B | 8 | 12 | 16 | 20 | 24 | 28 | 32 | 36 | 40 | 44 | 48 | 52 | Q4W 56-92 | Q8W 56-92 | 96 | 100 | Q4W After Week 100 | Q8W After Week 96 | 152 | | | | | |
| ISR Assessment for IM injections | X | | X | X | X | X | X | X | X | X | X | X | X | X | X | X | X | X | X | X | X | X | X | X | X | | |
| Columbia Suicide Severity Rating Scale (eC-SSRS) ^j | X | X | | X | X | | X | | X | | X | | X | | X | | X | | X | | | | | X | | | |
| Clinical chemistry and Hematology | X | X | X | X | X | | X | | X | | X | | X | | X | | X | | X | | X | | X | X | X | | |
| Pregnancy Testing ^k | S | U | S | U | S | U | S | U | S | U | S | U | S | U | S | S | U | S | S | U | S | S | S | S | | | |
| HIV-1 RNA and sample for storage (S) ^l | X | X | X | X | X | | X | | X | | X | | X | | X | S | | X | X | S | | X | X | X | | | |
| CD4+ cell count | X | X | | X | X | | X | | X | | X | | X | | X | | X | X | | | X | X | X | X | | | |
| CD8+ cell count | | X | | | | | | | X | | | | | | X | | | X | | | | X | X | | | | |
| Urinalysis ^m | | X | X | | | | | | X | | | | | | X | | | X | | | | X | X | | | | |

| Procedure | Screening Visit ^a | Maintenance Phase | | | | | | | | | | | | | | | | | | Extension Phase | | Withdrawal Assessments, ^y | Long-Term Follow-up ^z | |
|--|------------------------------|--|---------|------|----|----|----|----|----|----|----|----|----|----|----|-----------|-----------|----|-----|--------------------|-------------------|--------------------------------------|----------------------------------|--|
| | | Day 1 | | Week | | | | | | | | | | | | | | | | | | | | |
| | | Week 4A (Oral Lead-in Only) ^b | Week 4B | 8 | 12 | 16 | 20 | 24 | 28 | 32 | 36 | 40 | 44 | 48 | 52 | Q4W 56-92 | Q8W 56-92 | 96 | 100 | Q4W After Week 100 | Q8W After Week 96 | 152 | | |
| Fasting Lab Assessment: Glucose, Cholesterol (Total, HDL and LDL) and Triglycerides ⁿ | X | | | | | | | | | | | | | X | | | | | | | | X | X | |
| Hepatitis B (HBsAg), Anti-HBc, and Anti-HBsAG, Hepatitis C (anti-HCV Ab) | X | | | | | | | | | | | | | | | | | | | | | | | |
| PT/PTT/INR | X | X | | | | | | | | | | | | | | | | | | | | | | |
| PBMCs ^p | | X | | | | | | | | | | | | X | | | X | | | | | X | X | |
| Genetics sample ^q | | X | | | | | | | | | | | | | | | | | | | | | | |
| PK sampling ^r (S)=Storage only | | | X | X | S | X | S | X | S | X | S | X | S | X | S | S | S | X | S | | X | X | S | |

CONFIDENTIAL

207966

| Procedure | Screening Visit ^a | Maintenance Phase | | | | | | | | | | | | | | | | | | Extension Phase | | | Withdrawal Assessments, ^y Long-Term Follow-up ^z | | |
|--|------------------------------|--|---------|------|----|----|----|----|----|----|----|----|----|----|----|-----------|-----------|----|-----|--------------------|-------------------|-----|--|---|--|
| | | Day 1 | | Week | | | | | | | | | | | | | | | | | | | | | |
| | | Week 4A (Oral Lead-in Only) ^b | Week 4B | 8 | 12 | 16 | 20 | 24 | 28 | 32 | 36 | 40 | 44 | 48 | 52 | Q4W 56-92 | Q8W 56-92 | 96 | 100 | Q4W After Week 100 | Q8W After Week 96 | 152 | | | |
| Oral CAB and Oral RPV Dispensation ^s | | X | X | | | | | | | | | | | | | | | | | | | | | | |
| IP accountability (Pill Counts) ^s | | | X | X | | | | | | | | | | | | | | | | | | | | | |
| IM treatment administration when transitioning from SOC ^t | | | | X | X | X | X | X | X | X | X | X | X | X | X | X | X | X | X | X | X | X | X | | |
| IM treatment administration when transitioning from CAB + RPV LA Q4W | | X | | X | X | X | X | X | X | X | X | X | X | X | X | X | X | X | X | X | X | X | X | | |
| Patient Reported Outcomes ^u | | | | | | | | | | | | | | | | | | | | | | | | | |
| HAT-QoL (short-form) | | X | | | | | | X | | | | | | | X | | | | | | | | | X | |
| HIV TSQs | | X | | | | | | X | | | | | | | X | | | | | | | | X | X | |
| HIV TSQc ^v | | | | | | | | | | | | | | | X | | | | | | | | | X | |
| ACCEPT | | X | | | | | | X | | | | | | | X | | | | | | | | X | X | |

| Procedure | Screening Visit ^a | Day 1 | Maintenance Phase | | | | | | | | | | | | | | | Extension Phase | | Withdrawal Assessments, ^y | Long-Term Follow-up ^z | | |
|---|--|-------|--|---------|---|----|----|----|----|----|----|----|----|----|----------------|----|-----------|-----------------|----|--------------------------------------|----------------------------------|-------------------|-----|
| | | | Week 4A (Oral Lead-in Only) ^b | Week 4B | 8 | 12 | 16 | 20 | 24 | 28 | 32 | 36 | 40 | 44 | 48 | 52 | Q4W 56-92 | Q8W 56-92 | 96 | 100 | Q4W After Week 100 | Q8W After Week 96 | 152 |
| Reason for Switch or Reason for continuation ^w | X | | | | | | | | | | | | | | | | | | | | | | |
| Preference Questionnaires | | | | | | | | | | | | | | | X ^x | | | | | | X ^{aa} | X | |
| PIN | | | X | | | | X | | | | | | | X | | | | | | | X | X | |
| | Safety Follow Up Visit: Conduct approximately 4 weeks after the last dose of IP. Required only if the participant has ongoing AEs or lab abnormalities at the last on-study visit. This visit may be conducted by telephone. | | | | | | | | | | | | | | | | | | | | | | |

- a. Complete all Screening assessments within 35 days. Participants may begin the Maintenance Phase as soon as all Screening assessments are complete. Participants may be rescreened once and will be assigned a new participant number. Participants transitioning from the 201585 (ATLAS) study must reach ATLAS Week 48 (at minimum) prior to initiating Screening procedures for ATLAS-2M and must reach ATLAS Week 52 (at minimum) prior to randomization in ATLAS-2M.
- b. Visits Week 4a is part of the CAB + RPV Oral Lead-in period and is required only for participants transitioning from current SOC to CAB LA + RPV LA.
- c. Confirmation of eligibility to continue the Maintenance Phase and eligibility to enter the Extension Phase.
- d. Collect full routine medical history plus (report at Baseline visit): HIV risk factors (may be collected at a later study visit), cardiovascular risk factors (assessments include smoking status and history, family history of cardiac events), recent [\leq 6 months] illicit drug use, intravenous drug use, gastrointestinal disease, metabolic, psychiatric, renal, bone, and neurologic disorders.
- e. Physical exams should be conducted as part of normal routine clinical care. Medical assessments include any decisions the study staff must make for participants management and/or care of participant.
- f. Height collected at Baseline Day 1 only.
- g. Measure vital signs after about 5 minutes of rest in a semi-supine position.
- h. A 12-lead ECG will be performed after resting in a semi-supine position for at least 5 minutes. ECGs will be performed pre-dose. For participants transitioning from ATLAS, the pre-dose Week 48 ECG can also serve as the ATLAS-2M Screening ECG. ECG pre-dose will be performed in triplicate at

Day 1. A 2-hour post-dose ECG will also be performed at Days 1 and Week 48 for participants receiving CAB LA + RPV LA with an allowable window of ± 30 minutes.

- i. Only SAEs related to study participation or to a concomitantly administered ViiV/GSK product will be collected between obtaining informed consent and administration of study drug at Day 1.
- j. On Day 1, the eC-SSRS is to be administered prior to randomization. The eC-SSRS will preferably be completed at the beginning of the visit following administration of other PROs required prior to injections. The eC-SSRS is not required during the Withdrawal visit if withdrawal occurs during the Extension Phase.
- k. Women of childbearing potential only. SR=serum, UR=urine. Pregnancy events will be captured starting at Day 1 following initial exposure to study drug. Urine pregnancy test performed at Day 1 prior to administration of study drug, at Week 4B, and at study visits when other blood draws are not required in order to limit needle sticks. Serum pregnancy test can substitute for urine pregnancy test if locally required but must be appropriately timed to confirm pregnancy status prior to randomization and first IM administration.
- l. Week 48, Week 96 and Week 152 HIV-1 RNA retest (within 4 weeks) for results > 50 c/mL will be captured as unscheduled visit. Plasma for storage samples will be used for possible future analyses.
- m. A morning specimen is preferred. To assess biomarkers: urine albumin/creatinine ratio; urine protein/creatinine ratio; and urine phosphate. Urine phosphate results from visit 4a are not required by protocol to inform the safety review at visit 4b prior to receipt of initial CAB LA + RPV LA injections.
- n. An overnight fast is preferred; however, a minimum of a 6-hour fast is acceptable.
- o. Only collect if the Withdrawal visit occurs at Week 48, Week 96 or Week 152.
- p. Whole blood/PBMC collection samples may be used for virologic analyses. PBMCs will be collected at baseline Day 1, Week 48, Week 96, Week 152 or Withdrawal if prior to Week 152.
- q. Genetics sample should be collected only for patients who did not participate in the 201585(ATLAS) study (sample was previously collected and stored). Informed consent for genetic research must be obtained before sample collection. Sample may be collected at any visit after signing informed consent, but preferably at the Day 1 visit.
- r. One blood sample for CAB and RPV each to be collected at each PK timepoint. At Day 1, for participants from the ATLAS Q4W arm, PK samples are to be collected pre-dose relative to IM administration. At Week 4B, for participants randomized from SOC, Pre dose PK samples are to be collected: AFTER review of the PK diary to ensure that the samples are taken 20/28 hours after previous oral dose (diaries to be given at *Day 1 or W4a*); PRIOR to the final oral dose of CAB + RPV; PRIOR to the first IM injection.
- s. Only for Participants entering CAB + RPV Oral Treatment
- t. Participants switching to CAB LA + RPV LA will take final dose of oral lead-in regimen in the clinic at the Week 4B visit and begin injections. If possible, injections should be spaced approximately 2 cm from one another and from the site of any previous injection and or any injection site reaction. Bring RPV LA to approximately room temperature prior to injecting. Time and location of injection (right or left) as well as needle length used will be collected in the eCRF. The first injection can be performed as soon as central lab results become available and safety parameters are reviewed.

- u. All Patient Report Questionnaires/Surveys will be administered via paper instrument at the beginning of the visit before any other assessments are conducted and prior to administration of the eC-CSSRS. Conduct questionnaires/surveys at Withdrawal only if occurring at or prior to Week 152.
- v. The HIV-TSQc is to be administered to all participants transitioning from ATLAS and new participants transitioning from oral SOC. For participants transitioning from ATLAS, the version of the HIV-TSQc instrument to be administered will be based on the initial randomization arm at ATLAS Day 1.
- w. For patients randomized to oral SOC at Day 1 in ATLAS or new patients on SOC, the reasons for willingness to switch ART will be assessed at Day 1. For patients randomized to CAB LA + RPV LA Q4W in ATLAS, the reasons for willingness to continue long-acting ART in ATLAS-2M will be assessed at Day 1.
- x. Preference Questionnaire will be administered to all participants.
- y. Refer to Section 5.5 of the protocol for additional information on performing withdrawal assessments. HIV-1 RNA will be collected as Storage sample only if withdrawal assessments coincide with Week 52 or Week 100 or Week 156 (as per Section 5.5)
- z. Participants receiving one or more injections with CAB LA and/or RPV LA will be assessed with clinic visits at months 3, 6, 9 and 12 during the Long-Term Follow-Up Phase
- aa. Preference at Week 152 will be administered only to participants who received oral bridging during the Maintenance and/or Extension Phases

Note: BP – Blood pressure, HR – Heart Rate, HDL – High Density Lipoprotein, LDL – Low Density Lipoprotein, PT Prothrombin Time, PTT Partial Thromboplastin Time, INR International normalized ratio

